### **Changes to Schedule:**

#### **No-Show/Cancel**

1. Go to the [name] Lab Google Calendar and select appointment
2. Under **Title of Event**, type in **No Show** or **Canceled**
3. Attempt to reschedule participant
4. Once a reschedule has been confirmed, follow the instructions below

#### **Reschedule**

1. Go to the [name] Lab Google Calendar and select appointment
2. Under **Title of Event**, type in **“Rescheduled”** once the appointment is rescheduled.
3. Change the appointment time and duration.
4. Select save and make sure the appointment appears on the **NRT Sampling Calendar**.
5. If you are adjusting by a whole week or more, select “Yes, adjust all dates” and be sure to adjust any that fall on weekends or days you are not available
6. If you are changing an appointment by a day or two and subsequent appointments will not be affected, select “No, just this one”
7. Double check your calendar against other appointments, and make sure you have no future conflicts

#### **Box.com**

Go to [www.uab.edu/adminsys](http://www.uab.edu/adminsys) and log into the Box.com on the Surface Pro under your blazerid and password. Then proceed with the following steps:

#### **Log-In Information:**

BlazerID:

Password:

### **Nicotine Patch**

- Nicotine patches (21, 14, or 7 mg): One box contains 14 patches.
- 21 mg : For participants who self-report smoking *over 10 CPD*
- 14 mg: For participants who self- report smoking *10 or less CPD*
- 7 mg: Lowest-dose patch and dispensed at Week 9

### **Nicotine Gum**

- Nicotine gum (2 or 4 mg): One box contains 110 pieces
- 4 mg: For participants who self-report smoking first cigarette within 30 minutes after awakening (reported on Fagerström Test for Nicotine Dependence at Baseline)
- 2 mg: For participants who self-report smoking first cigarette more than 30 minutes after awakening (reported on Fagerström Test for Nicotine Dependence at Baseline)

### **Nicotine Lozenge**

- Nicotine lozenges (2 or 4 mg, mint flavor): One box contains 3 Quit Tubes, with 24 lozenges per tube, for a total of 72 lozenges per box.
- 4 mg: For participants who self-report smoking first cigarette within 30 minutes after awakening (reported on Fagerström Test for Nicotine Dependence at Baseline)
- 2 mg: For participants who self-report smoking first cigarette more than 30 minutes after awakening (reported on Fagerström Test for Nicotine Dependence at Baseline)
- Participants are encouraged to use 8-10 lozenges per day, and at most 20 per day

### **Nicotine Inhaler**

- One box contains the device and 168 cartridges
- 4mg (20 minutes of active puffing): For participants who self-report smoking first cigarette within 30 minutes after awakening (reported on Fagerström Test for Nicotine Dependence at Baseline)

- 2mg (10 minutes of active puffing): For participants who self-report smoking first cigarette more than 30 minutes after awakening (reported on Fagerström Test for Nicotine Dependence at Baseline)

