### Intervention Group A

Week 1:

7 patches (dose based on # of cigarettes smoked per day as reported by subject at Baseline)  
11 blister packs of gum (dose based on if subject reports at Baseline smoking first cigarette within 30 minutes of waking)

Week 2:

7 patches (dose based on # of cigarettes smoked per day as reported by subject at Baseline)  
1 box inhaler and cartridges

Week 3:

7 patches (dose based on # of cigarettes smoked per day as reported by subject at Baseline)  
1 nasal spray bottle

Week 4:

7 patches (dose based on # of cigarettes smoked per day as reported by subject at Baseline)  
2 quit tubes of baseline-indicated lozenge dose, and 1 quit tube of the other dose (for approx. 8-10/day, with both doses to try, e.g., if subject reports at Baseline smoking first cigarette within 30 minutes of awakening, he or she will receive 2 tubes of the 4 mg dose and 1 tube of the 2 mg dose).

Week 5:

7 patches (dose based on # of cigarettes smoked per day as reported by subject at Baseline)  
Participant's selection of short-acting NRT (week long supply)

Week 6:

21 patches (dose based on # of cigarettes smoked per day as reported by subject at Baseline)  
Participant's selection of short-acting NRT (3 week supply)

Week 9:

28 patches  
Participant's selection of short-acting NRT (4 week supply)

\*21 mg participants will begin to taper dose. They will receive 2 weeks' worth of 14 mg patches and 2 weeks' worth of 7 mg patches.

\*\*14 mg participants will receive 4 weeks of 7mg patches.

\*\*Participants using gum or lozenges will taper amount used. They will use half of their original amount for the first two weeks and  $\frac{1}{4}$  of their original amount for the next two weeks.

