Combination Nicotine Replacement (cNRT). Participants will be screened at the time of their baseline appointment for the appropriateness of all NRT products. Our physician collaborator will be available to answer any questions that may arise when screening participants and will assist the PI in evaluating any adverse events believed to be related to the use of NRT. All participants will be evaluated for their initial NRT dose based on Federal Drug Administration guidelines. Participants who smoke 10 or fewer cpd will start at 14mg patch while smokers who use 11 or more cpd will start at 21mg patch. The nicotine inhaler delivers 4 mg of nicotine per cartridge (inhaling for 20 minutes on each cartridge) with participants using about 6 cartridges daily. Nicotine nasal spray delivers 0.5mg of nicotine per spray with one spray per nostril (1mg total) recommended 1-2 times per hour. Participants will be given the 2mg nicotine gum or lozenge to use. The safety and tolerability of using NRT products together or smoking while using NRT has been demonstrated^{e.g.51}. Further, the rationale for using combination NRT over a single agent is two-fold. First combination NRT has demonstrated the best efficacy for promoting abstinence over all other single agents with the exception of varenicline⁵⁸. Second, NRT is short-acting and can be administered in-session to demonstrate the effect of this medication in relieving withdrawal symptoms, including craving. NRT can also be used sporadically as is proposed during the sampling weeks. Other smoking cessation pharmacotherapies (e.g., bupropion, varenicline) take about a week to titrate to full effect²⁶. Both groups will receive 8 weeks of medication for a sustained quit attempt, although the In vivo group will be sampling four different short acting NRT products during the first four weeks of the intervention.

Baseline and Assessment Measures. After eligibility determination and consent to participate, the baseline assessment will be administered. This assessment is expected to take about 60 minutes and will provide basic smoking history, smoking behavior, and proposed mediators and moderators such as treatment interest, expectancies for NRT, previous use of NRT, craving, withdrawal, and side effects associated with NRT use (see Table 1 description) and will be repeated during the study period (see Table 2 for assessment schedule).

Table 1: Instrument Description

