Credibility and Expectancy Questionnaire (CEQ) ⁶⁹ . This 6-item brief scale asks patients about how they think and feel about the treatment. It is broken down into two main scales; credibility and expectancy for treatment. It has demonstrated good internal consistency and good test-retest reliability. (2 min).
Side Effects . We will use a side effect scale to determine common side effects associated with pharmacotherapy and quitting smoking. This self-administered, 1-7 Likert scale instrument was used during our previous smoking cessation trial with correctional populations and captured the range of side effects experienced during the trial. (5 min)
Carbon Monoxide (CO) and Tobacco Use Assessment . Expired breath samples will be obtained at every study visit. Participants will be asked questions related to recent smoking behavior, including time since last cigarette, 24 hour quit attempts, overnight abstinence status, number of cpd, and average cpd smoked for that week. CO >3 ppm will be considered smoking ⁷⁰⁻⁷² . (1 min)
NRT Adherence . All participants will be assessed on their self-reported daily use of NRT using a Time Line Follow-Back (TLFB) method during the 8 weeks of treatment. All participants will also be assessed during all intervention weeks for their use of NRT by returning used patches and returning used blister packaging/used canisters/cartridges from short-acting NRT. Use of 80% of more of the medication will be considered adherent. We used a similar technique to assess NRT adherence in our pilot trial with good compliance with returning used patches/blister packaging. (5 min)

Table 2: Study

Assessment Schedule	BL	Post-Randomization Assessment Schedule								
		WK1 S1 (\$20)	WK2 S2 (\$20)	WK3 S3 (\$20)	WK4 S4 (\$20)	WK5 PS (\$20)	WK6	WK9	WK13	M1 FU (\$40)
Measures or Procedures (weekly compensation)	Day 0 (\$10)									
Screening Questionnaire	X									
Demographics	X									
Urine Drug Screen	X									
Smoking History	X									
Treatment Expectancies	X	X	X	X	X	X	X	X	X	
PSS – 10 Item	X	X	X	X	X	X	X	X	X	
TAA	X	X	X	X	X	X	X	X	X	
SAQ	X				X	X	X	X	X	
ARME	X	X	X	X	X	X	X	X	X	
ANRT-12	X	X	X	X	X	X	X	X	X	
FTND	X				X	X	X	X	X	
WISDM	X				X	X	X	X	X	
QSU	X	X ¹	X ¹	X ¹	X ¹	X	X	X	X	
MNWS	X	X ¹	X ¹	X ¹	X ¹	X	X	X	X	
TSS						X			X	X
CEQ						X			X	X
Side Effects	X	X	X	X	X	X	X	X	X	
Carbon Monoxide (CO)	X	X	X	X	X	X	X	X	X	

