NRT Adherence	X	X	X	X	X	X	X	X	X	

Note: BL=Baseline Assessment; S=session; WK=week; M=month; PS=Product Selection; ¹All participants will complete these surveys twice (at the beginning and end of session) during sessions 1-4.

Randomization. We anticipate enrolling 10 pre-pilot participants in 3 months and 80 participants in 20 months and, based on our previous study with this population, expect to retain at least 70% through the one month follow-up point. Randomization will occur after completion of the initial screening and assessment.

Primary Outcomes. Feasibility and acceptability will be measured through high study retention (70%) and recruitment (recruitment of all participants within 24 months) in our groups. Additional items of acceptability include high scores on treatment satisfaction and credibility/expectancies that are equal or higher to the SC

group. Medication adherence is a third primary outcome with expected differences between our groups. Adherence is notoriously difficult to determine. Self-reported adherence is not always reliable, particularly during treatment studies where there is a demand characteristic to report the desired targeted behavior⁷³⁻⁷⁴ (e.g., adherence to NRT). The behavioral methods described under the assessment section represent the best available self-report tools for determining NRT adherence (e.g., TLFB report, returning used NRT patches and used product blister packs/packaging). Adherence will be defined by self-report using the TLFB and verified through returned patches and packaging. Good adherence is defined by taking greater than 80% of doses of medication at each time point. We have used these techniques in previous studies with low income populations with good compliance for use of TLFB verified by return of NRT materials⁷⁵.

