To test Aim 3, we will examine medication adherence during the 8 week intervention period between the intervention groups using Chi Square analyses at weeks 6, 9 and 13. Medication adherence will be defined as a self-reported use of taking 80% of medication as prescribed at each time point for both groups (adherent or not adherent). We can also look at adherence as a continuous proportion variable: adherence = number of doses taken / the number of doses given. We will also examine demographic and smoking characteristics (particularly withdrawal, cravings, abstinence self-efficacy, and NRT perceptions) that would be associated with medication adherence at weeks 6, 9 and 13 using logistic regression. These analyses will allow us to examine important associations with medication adherence in these groups.

To examine underlying factors believed to be important for medication adherence, particularly withdrawal, craving, self-efficacy, and perceptions of NRT, we will also examine these factors by intervention groups across time using paired t-tests, as appropriate. We are primarily interested in determining if our In vivo group had decreases in withdrawal and cravings, while increasing abstinence self-efficacy and NRT perceptions relative to the SC group. Given the pilot nature of this intervention, we will be able to examine 24-hour quit attempts and abstinence, but these factors are not the main focus on analyses as we will likely be underpowered to find significant differences on these outcomes with this small of a sample. While 80 participants may seem like a fairly large sample for a pilot study, a sample size between 500-600 participants is typical for most smoking cessation interventions and would be needed to examine important moderators and mediators of cessation. However, we will be able to obtain initial effect sizes that will be useful for determining the appropriate sample size for a fully-scaled R01 project in the future, if this intervention appears promising.

Missing data. There is a high likelihood that we will have participants who may miss an appointment, do not complete the study, or are otherwise lost to follow-up. Because of the potential of bias due to non-missing

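### Dividing doses taken by doses given can score a compliant user below 80%, depending on product and pack size; the SAP should fix one denominator, the doses instructed

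*Protocol*

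**What the plan says.** Medication adherence is one of the SAP's primary outcomes (Primary Outcomes). Its denominator is worded in four ways:

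- **Table 1, NRT Adherence:** "Use of 80% of more of the medication will be considered adherent".
- **Primary Outcomes:** "Good adherence is defined by taking greater than 80% of doses of medication at each time point".
- **Data Management and Statistical Analysis, Aim 3, main binary definition:** "Medication adherence will be defined as a self-reported use of taking 80% of medication as prescribed at each time point for both groups". This is compared between arms "using Chi Square analyses at weeks 6, 9 and 13".
- **Same paragraph, offered as an additional continuous measure:** "adherence = number of doses taken / the number of doses given".

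On supply and use:

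- **Inhaler.** The Protocol's Nicotine Inhaler section says "One box contains the device and 168 cartridges". The Medication Dispensing section gives In vivo participants one such box for a single sampling week. The SAP's cNRT section describes "participants using about 6 cartridges daily".
- **Lozenge.** The Protocol encourages 8-10 a day. The Therapy Protocol hands out 72 for a sampling week.
- **After selection.** The short-acting product is supplied for one week at Week 5, three weeks at Week 6 and four weeks at Week 9, with no unit counts.
- **Taper.** Under Groups A-D at Week 9, on gum and lozenge users: "They will use half of their original amount for the first two weeks", then a quarter for the next two. The Control Group dispensing section has no such line. The Week 9 visit procedure, common to all arms, refers to taper guidance in a therapist manual that is not among the documents.
- **Choice of product.** In vivo participants choose after sampling all four products. SC participants choose from a description (SAP, Product Selection).

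**The concern.** A ratio of taken to given measures adherence only when the amount given equals the amount the participant was told to take. If more is handed out, because products come in fixed packs or because a taper lowers the instruction but not the supply, someone who follows instructions exactly scores below 100% and may fall under the 80% cut. The shortfall depends on the product.

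Product is chosen after randomisation, by sampling in one arm and by description in the other. If the mix differed by arm, part of any measured difference in adherence could come from packaging. Leftover stock is a second possible route. A sampling-week inhaler box used at 6 cartridges a day leaves 168 - 42 = 126 cartridges, and unused ones may be handed back, whereas SC participants receive no medication in Weeks 1-4. The pilot's effect sizes are meant to inform the sample size of a larger trial, so the denominator matters beyond this study.

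**Working it through.** The plan states no expected adherence percentage on this point, so there is no figure to reproduce. The check asks what a fully compliant participant scores when the denominator is supply.

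**Lozenge, one week.** Inputs: 8-10 a day (Protocol, Nicotine Lozenge); 72 given (the sampling-week quantity, assumed to continue after Week 5).
- 8 a day: 8 × 7 / 72 = 56/72 = 77.8%, below the cut.
- 10 a day: 70/72 = 97.2%.
- The edge of the rule also matters. If the denominator were 10 a day, 8 a day gives 56/70 = 80.0% exactly. That is adherent under Table 1 and not adherent under Primary Outcomes.

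**Gum or lozenge, Weeks 9-13.** Inputs: half the original amount for two weeks, then a quarter for two; four-week supply assumed untapered.
- (2 × 1/2 + 2 × 1/4) / 4 = 1.5/4 = 37.5%.
- Supply cut to the taper: 100%.
- Rounding to packs matters too. Tapered use from 8-10 lozenges a day is 8 × 28 × 0.375 = 84 to 10 × 28 × 0.375 = 105. From two boxes (144) this scores 58.3% to 72.9%. From whole tubes of 24 it is 84/96 or 105/120, both 87.5%.

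**Inhaler.** Inputs: 6 cartridges a day (SAP, where the figure is approximate); one 168-cartridge box assumed at each of Weeks 5, 6 and 9.

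| Read at | Used | Given | Ratio |
|---|---|---|---|
| Week 6 | 6 × 7 = 42 | 168 | 25% |
| Week 9 | 6 × 21 = 126 | 168 | 75% |
| Week 13 | 6 × 28 = 168 | 168 | 100% |
| All 8 weeks | 336 | 504 | 66.7% |

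If cartridges are counted out as 42, 126 and 168, each ratio is 100%. If one box covers Weeks 5-9 (42 + 126 = 168) and another covers Weeks 9-13, the eight-week ratio is 336/336 = 100%.

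**Possible effect on the arm comparison.** Assume whole-box dispensing, the ratio cut at 80%, all other products scored correctly, and equal true adherence in both arms. The spurious gap at Week 6 is then true adherence × difference in inhaler share.
- True adherence 40%; 10% of In vivo and 30% of SC choose the inhaler: 0.40 × 0.90 = 36% against 0.40 × 0.70 = 28%, a gap of 8 points.
- Share differences of 10 to 30 points: 4 to 12 points at 40% true adherence, and 10 to 30 points at 100%.
- Uncut mean ratio with everyone compliant: 0.75 × 10 to 30 = 7.5 to 22.5 points at Week 6, and 0.25 × 10 to 30 = 2.5 to 7.5 points at Week 9.

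True adherence and the inhaler shares are assumptions; neither document gives product shares by arm.

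**The case against.** The strongest reply is that the controlling definition is already right. The binary outcome tested by chi-square is use as prescribed. Read literally, it scores a compliant inhaler or tapering user as adherent. The taken/given ratio is only something that may also be examined, with no threshold or arm comparison attached. This stands, and it limits the point. It does not close it. Table 1 and Primary Outcomes state the 80% rule without those words, and the prescribed count is not a single number in these documents: a range for lozenges, an approximate figure for the inhaler, one to two times an hour for the spray, and no daily figure for gum. Instruction sheets and workbooks that were not supplied may settle it. The unit count that staff are told to log is what was handed out (Medication Inventory), so supply is the easy default.

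Second, the dispensing assumptions may be false. Whole inhaler boxes are specified only in In vivo sampling weeks, outside the eight-week adherence period. From Week 5 the inventory step lists cartridges, and staff give enough to reach the next visit. The 75% needs a further full box at Week 6 although 126 cartridges would remain from the first. The Week 9 step may size the supply to the taper. A dose also need not be a cartridge, since the Protocol describes 10-minute and 20-minute inhaler doses. All of this stands, so every percentage above is conditional.

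A reader might go further and infer that compliant inhaler users will score 25-75%, that tapering users will score 37.5%, and that the primary comparison is therefore biased. The documents do not support that. They do not give the quantities dispensed after selection, the inhaler figure reaches 100% at Week 13 under the same assumption, and no difference in product mix by arm is shown.

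**Conclusion.** The point holds in conditional form. The SAP leaves the adherence denominator unsettled, and its one explicit formula uses supply. Under that formula a fully compliant participant can score 77.8% (lozenge at 8 a day from 72 a week), 37.5% (gum or lozenge in Weeks 9-13, untapered supply) or 25% and 75% (inhaler at Weeks 6 and 9, whole box each visit, 6 a day). If supply equals the instructed amount, there is no artefact. Bias between arms is possible because product choice follows randomisation and is made differently in each arm, but neither its size nor its direction can be known from the documents. The main binary outcome is safe if medication as prescribed is applied literally with a defined count. The change is worth making because it is cheap and protects a primary outcome.

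**What to change.** 1. In the SAP, define one denominator: doses the participant was instructed to take in the interval, by product and including any taper. Use it for the continuous measure and for the 80% rule in Table 1, Primary Outcomes and Aim 3. Cap the ratio at 100%.
2. State whether the cut is at least 80% or above 80%. Where the instruction is a range, name in advance the value that forms the denominator. Define the counting unit for each product.
3. Record the instructed number of doses on the Medication Given form at each dispensing visit.
4. Report the share of supply used only descriptively.
5. Reconcile the Protocol's Medication Dispensing sections, its Week 9 visit procedure and the SAP's cNRT section, including whether the gum and lozenge taper written under Groups A-D applies to Control. This needs no change to any dose.

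The cost is SAP wording and one field on an existing form. The downside is that staff must fill in that extra field.

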### Nicotine Nasal Spray

- One box contains four 10ml bottles
- 2mg: 2 sprays (1mg) in each nostril

### Medication Ordering

The patches, gum, lozenges, inhalers, and nasal spray are ordered from The Kirklin Clinic (TKC) in bulk prescriptions.

1. Order 75 boxes of 21mg patches at a time, or as needed
2. Order 90 boxes of 14mg patches at a time, or as needed
3. Order 90 boxes of 7mg patches at a time, or as needed
4. Order 15 boxes of 4mg nicotine gum at a time, or as needed
5. Order 15 boxes of 2mg nicotine gum at a time, or as needed
6. Order 15 boxes of 4mg mint lozenges at a time, or as needed
7. Order 15 boxes of 2mg mint lozenges at a time, or as needed
8. Order 15 boxes of inhalers at a time, or as needed
9. Order 15 boxes of nasal spray at a time, or as needed
10. The respective blank RX form(s) and “Pharmacy Memo” should be completed and scanned to [name] assistant for his signature
11. The scanner can be found in the break room
12. Send the documents to [name] assistant [name]: [contact], with the subject line: **[name] Smoking Cessation RX- Signature Requested**
13. [name] assistant will then send the signed RX back and then should be faxed along with the memo to TKC.
14. Allow 24 hours for the pharmacy to prepare the bulk prescription
15. Call pharmacy to confirm prescription is ready prior to picking up

